4.8.2 All other visit Windows

Participants may attend sessions up to four-calendar day's pre or post the scheduled visit.

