A study published in 2012 evaluated the efficacy of combining hydroxyzine with ondansetron for treatment of side effects associated with chemotherapy regiments which utilized highly emetogenic drugs. This study demonstrated that complete control of acute emesis was achieved in 56% of pediatric cancer patients utilizing both antiemetic medications versus only 22% utilizing ondansetron without hydroxyzine (p=0.006). This study also reported that patients and parents noted "...significantly better sleeping quality, appetite, activity and mood..." for those patients taking ondansetron with hydroxyzine versus without hydroxyzine. The dose of hydroxyzine used was 1 mg/kg/dose, equivalent to 77 mg for an average adult female and 89 mg for an average adult male (an average American female weighs 170 lbs. and an average American male weighs 197 lbs. according to the CDC). Dosing for this study will be based on minimizing the risk of sedation (25 mg AM dosing) while optimizing the beneficial effects of the study drug (50 mg PM dosing). Participants will be titrated to these doses in a similar fashion as the titration of varenicline, allowing for dose adjustment based on daily evaluation of potential side effects.

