5.3 Dosage

- First 3 days of treatment: PM two 25 mg tablet orally.
- Starting on the fourth day of treatment and continuing until the EOS: AM one 25 mg tablet orally; PM two 25 mg tablets orally.
- Dosing will be adjusted based on reported side effects.

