5.4 Dose Adjustment Procedures

Dose adjustments for hydroxyzine will be performed by licensed medical providers based on adverse effects reported by participants (e.g. daytime sedation...stop the AM dose of hydroxyzine, difficulty waking in the am...decrease nighttime dose of hydroxyzine). Participants will be contacted with a follow-up call by Research Medical Staff within 72 hours of any dose adjustment.

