7.2.14.12 Review of Systems

The Review of Systems is an internal questionnaire administered at screening (V1) to help assess the participant's current health and health history by asking about the presence of a list of symptoms.

7.2.14.13 *Employment History*

The Employment History is an internal questionnaire designed to collect information about a participants' social economic status. Participants will be presented this questionnaire after enrollment, at the second visit (V2).

7.2.14.14 *Adverse Effects*

During each visit after enrollment (V2 through V7), participants will respond to adverse events based on a mild/moderate/severe rating. The questionnaire will use both targeted questions and open-ended questions to access for any adverse effects/events. Participants will respond to SMS text message inquiries for study specific adverse effects, on a daily basis, commencing after enrollment (see Section 8.8).

7.2.14.15 *Medication Compliance*

Participants will be queried via SMS text messages whether they have been compliant with taking the study specific medications. These messages will commence after the second visit and continue through the End of Study (see Section 8.8).

7.2.14.16 *Smoking Status*

SMS text messages will be sent to participants starting after enrollment, through the End of Study, to ascertain the participants smoking status (see Section 8.8).

8 Sessions

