8.1 SCREENING SESSION (V1)

Eligibility of participants to participate in this study will be assessed at the screening visit (V1). The ICF will be signed, dated and timed prior to any other screening procedures (see Section 8.5).

The sequence of the following assessments will be at the discretion of the Investigator (or designee) after signature of the ICF.

- Questionnaires
 - Smoking History
 - Registration Form
 - Medical History (with Review of Systems)
 - Patient Health Questionnaire (PHQ-9)
- Prior and Concomitant Medication
- Expired air CO breath test
- Urine collection for urinalysis and drug screen
- Vital signs (blood pressure, heart rate, respiratory rate)
- Height and weight / BMI
- Temperature
- Electrocardiogram (ECG)
- Physical examination

- Blood collection for safety laboratory testing (including pregnancy test for females)
- Instructions on use of the SMS messaging/questionnaire system

8.2 5-DAY OBSERVATION PERIOD

After verification of eligibility (approximately two days after screening), participants will be enrolled in the study and commence a five-day observational period. Participants will be called and given instructions on the use of the SMS system which will administer questions about adverse effects and smoking status in order to collect baseline data prior to start of the study drugs.

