8.7 SCHEDULE OF EVENTS

Visit Assessments and Procedures		Screening Session	5-day observation period	Laboratory Sessions						6-month f/u
		V1		V2	V3	V4	V5	V6	V7	
Informed Consent and Guidance		•								
Inclusion/Exclusion Criteria		•								
Enrollment			•*							
Prior and Concomitant Medication		•		•	•	•	•	•	•	
Questionnaires	Smoking History Questionnaire	•								
	Registration Form	•								
	Employment History			•						
	Medical History/Review of Systems	•								
	10-item Perceived Stress Scale (PSS-10)			•	•	•	•	•	•	
	6-Item State-Trait Inventory			•	•	•	•	•	•	
	Wisconsin-Predicting Patient's Relapse (WI-PREPARE)			•	•					
	Modified Cigarette Evaluation Questionnaire (mCEQ)			•	•					
	The Fagerström Test for Nicotine Dependence (FTND)			•	•	•	•	•	•	
	Patient Health Questionnaire (PHQ-9)	•		•	•	•	•	•	•	
	Minnesota Nicotine Withdrawal Scale (MNWS)					•	•	•	•	
	Smoking Status (via daily SMS text)		•	•	•	•	•	•	•	•
	Medication Compliance (via daily SMS text)			•	•	•	•	•	•	
	Adverse Effects Questionnaire (at visits and daily SMS Text)		•	•	•	•	•	•	•	
	Safety Laboratories	•								
Serum Pregnancy Test (Females)		•								
Urine Pregnancy Test (Females)				•	•	•	•	•	•	
Urine Drug Screen		•								
CO Breath Test		•		•	•	•	•	•	•	
	ECG	•								
Vitals	Blood Pressure	•		•	•	•	•	•	•	
	Heart rate	•		•	•	•	•	•	•	
	Temperature	•								
	Respiratory rate	•		•	•	•	•	•	•	
	Weight	•		•	•	•	•	•	•	
Height		•								
BMI		•								
Physical Examination		•		•#	•#	•#	•#	•#	•#	
Collect Used/Unused Blister Packs					•	•	•	•	•	
Dispense Study Drugs in Blister Packs				•	•	•	•	•		

^{*}After evaluation of safety labs, prior to start of observational period

[#] Targeted examination as needed

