8.8 SMS Messaging

- 8.8.1 Daily SMS Message (after enrollment, prior to V2) Participants will receive a text with a link to a survey to access the following:
 - How soon after you wake up did you smoke your first cigarette?
 - 1-Within 5 Minutes, 2-6 to 30 Minutes, 3-31 to 60 Minutes, 4-After 60 Minutes
 - How many cigarettes did you smoke today?
 - What was your level of stress today?
 - 1-No Stress, 2-Mild Stress, 3-Moderate Stress, 4-A Lot of Stress, 5-Extreme Stress
 - · How well did you sleep last night?
 - 1-No problems, 2-Mild problems, 3-Moderate problems, 4-A Lot of problems, 5-Extreme problems
 - Did you feel nauseated today?
 1-No nausea, 2-Mild nausea, 3-Moderate nausea, 4-A lot of nausea, 5-Extreme nausea
- 8.8.2 Daily SMS Message (after Visit 2) -- Participants will receive a text with a link to a survey to assess the following:
 - Have you smoked any cigarettes today?
 - If yes, how soon after you wake up did you smoke your first cigarette?
 1-Within 5 Minutes, 2-6 to 30 Minutes, 3-31 to 60 Minutes, 4-After 60 Minutes
 - O How many cigarettes did you smoke today?
 - Did you take your study drugs this morning?
 - Did you take your study drugs this evening?
 - What was your level of stress today?
 - 1-No Stress, 2-Mild Stress, 3-Moderate Stress, 4-A Lot of Stress, 5-Extreme Stress
 - How well did you sleep last night?
 - 1-No problems, 2-Mild problems, 3-Moderate problems, 4-A Lot of problems, 5-Extreme problems
 - Did you feel nauseated today?
 - 1-No nausea, 2-Mild nausea, 3-Moderate nausea, 4-A lot of nausea, 5-Extreme nausea
- 8.8.3 6-Month follow up SMS Message -- Participants will receive a text with a link to a survey to assess the following:
 - Have you smoked a cigarette since your last visit?
 - o If yes, are you still smoking cigarettes right now?

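### Section 5.1 bases hydroxyzine dose adjustment on daily side-effect evaluation, but the daily survey has no drowsiness or difficulty-waking item; the first scheduled on-drug question comes at V3

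*Combined protocol and SAP*

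**What the plan says.** Section 5.1 closes its dosing rationale by saying that participants will be titrated in step with varenicline, "allowing for dose adjustment based on daily evaluation of potential side effects". The sentence before gives minimizing sedation as the reason for the 25 mg morning dose. Earlier, section 5.1 names drowsiness as the hydroxyzine effect seen in 10% or more of users and puts all others below 10% or at unknown incidence.

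Section 5.3 sets the timing: "Starting on the fourth day of treatment and continuing until the EOS: AM one 25 mg tablet orally". Section 5.4 gives two examples of adjustment: "daytime sedation...stop the AM dose of hydroxyzine, difficulty waking in the am...decrease nighttime dose of hydroxyzine".

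On data collection, section 7.2.14.14 states: "Participants will respond to SMS text message inquiries for study specific adverse effects, on a daily basis". It refers to section 8.8 for the content. The row in the section 8.7 schedule is labelled "Adverse Effects Questionnaire (at visits and daily SMS Text". Section 8.2 says the SMS system in the observation period is one "which will administer questions about adverse effects and smoking status in order to collect baseline data prior to start of the study drugs".

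Section 8.8.2 and Appendix 14 fix what is asked each day on drug: smoking, morning and evening doses taken, stress, sleep and nausea. Drowsiness appears on the visit Adverse Effects Form (Appendix 13), given at V2 to V7.

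**The concern.** The symptoms that are meant to drive hydroxyzine dose changes are not among those asked about daily. The sleep item does not stand in for them. It asks about problems with the night's sleep, so an over-sedated participant could truthfully answer that there were none.

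Titration is the period for which section 5.1 states daily evaluation, and the morning dose is introduced within it. If the survey is run as written, it gives medical staff no scheduled information on sedation until V3. What is at stake is timely dose adjustment for the one hydroxyzine effect the plan lists as common. No efficacy or decision quantity is involved.

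**Working it through.** The plan states no figure on this point, so there is none to reproduce. The check compares the items on the two instruments and then counts doses against visit days.

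**Items**

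| Symptom | Daily survey (8.8.2, App. 14) | Visit form (App. 13) |
|---|---|---|
| Nausea | yes | yes |
| Drowsiness | no | yes |
| Fatigue | no | yes |
| Headache | no | yes |
| Vomiting | no | yes |
| Unusual heart rate | no | yes |
| Difficulty waking | no | not listed |
| Open-ended field | no | yes |

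One of the six listed effects on the visit form is in the daily survey.

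**Inputs**

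- Study drugs are first dispensed at V2 (section 3.3), so the V2 form is completed before any dose.
- V3 is d = 6 days after starting medication (section 8.4).
- The evening dose starts on treatment day 1 and the morning dose on treatment day 4 (section 5.3).
- Visit window (section 4.8.2): "Participants may attend sessions up to four-calendar day's pre or post the scheduled visit".
- Assumption: the first dose is taken on the evening of V2, which is treatment day 1. V3 then falls on treatment day d + 1 = 7.

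**Doses before the V3 question**

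- Evening doses = d = 6.
- Morning doses on days 4, 5 and 6: d − 3 = 3. Adding the morning of V3 gives d − 2 = 4.
- Daily surveys on treatment days 1 to 6 = 6. All ask about nausea; none asks about drowsiness.

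**Sensitivity**

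- Window, earliest (d = 6 − 4 = 2): 2 evening doses and 0 morning doses.
- Window, latest (d = 6 + 4 = 10): 10 evening doses and 7 to 8 morning doses.
- If six days is counted inclusively, V3 is treatment day 6 (d = 5): 5 evening doses and 2 to 3 morning doses.

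**Later gaps between visit forms** (days after the first dose)

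- Quit date = 7. V4 = 7 + 14 = 21. V5 = 21 + 28 = 49.
- V3 to V4 = 21 − 6 = 15 days. V4 to V5 = 49 − 21 = 28 days.
- Section 8.5 gives 4-week intervals from then on. Four post-quit visits on that pattern fall at weeks 2, 6, 10 and 14, which is past the 12-week treatment period. The V6 to V7 gap is therefore unclear and is not relied on here.

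**The case against.** The strongest case is that the operative rules do not depend on the survey. Sections 5.3 and 5.4 act on side effects that participants report. The phrase about daily evaluation occurs once, in a rationale paragraph, and names no instrument. Section 2.1.4 openly divides the work, with targeted and open-ended questions at visits and nausea by daily SMS. Section 7.2.14.14 limits the daily questions to study-specific effects.

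Section 9.4 tells participants to report any side effect, has staff pass reports on at once, and gives a 24-hour number. Drowsiness is something a participant notices without being tested for it. The V3 form covers the whole interval since V2. Appendix 17, the hydroxyzine instructions, is not in the text available and may tell participants to report sedation. On this view, rewording section 5.1 would be enough.

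Much of this stands. Sedation is not unmonitored, section 5.4 can be followed as written, and nausea and sleep are themselves asked about daily. At the early edge of the visit window V3 can also precede the first morning dose.

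None of it supplies the daily evaluation that section 5.1 states for the symptoms section 5.4 names. Unprompted reporting is not scheduled evaluation. The 72-hour call in section 5.4 follows an adjustment, so it cannot detect the first sign. Instructions in Appendix 17 would not add a survey item. If the section 8.7 label means that the full form goes out daily, then section 8.8.2 and Appendix 14 are what need correcting.

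**Conclusion.** The concern holds and is minor. On the nominal schedule, participants take 6 evening and 3 to 4 morning hydroxyzine doses before anyone is scheduled to ask about drowsiness on drug. Across the visit window the range is 2 to 10 evening and 0 to 8 morning doses. These counts assume a first dose on the evening of V2.

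The documents give no basis for estimating how many dose adjustments would be delayed, and none is claimed. The nausea rule in section 13.1.2 and the error rates in section 13.1.3 do not use drowsiness, so the decision to proceed to a randomized trial is untouched.

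**What to change.** Add one row, *Drowsiness or difficulty waking*, on the existing scale from None to Extreme, to the daily survey in section 8.8.2 and Appendix 14. Add the same row to the observation survey in section 8.8.1 and Appendix 16, so that there is a pre-drug baseline on the same daily scale.

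In section 5.4, add a sentence saying that medical staff review these answers when considering the hydroxyzine dose. Leave any threshold for calling the participant to the medical lead. The sentence is needed because the visit lists in sections 8.4 and 8.5 specify review of SMS answers only for smoking status and medication compliance.

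The cost is one more daily question in two existing surveys, the sentence in section 5.4 and some staff time for review. No extra participants, visits or samples are needed. Rewording section 5.1 to refer to reported side effects would remove the inconsistency but would give staff no earlier information on sedation, so it is the weaker option.

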5.2 Hydroxyzine Product Use Timeframe

Dosing will begin one week before a target quit-smoking date and will continue for a total of approximately 12 weeks, the same duration as the FDA-approved dosing for varenicline. Since hydroxyzine does not demonstrate any dependence or addictive properties, there is no indication to taper the dose.

5.3 Dosage

- First 3 days of treatment: PM two 25 mg tablet orally.
- Starting on the fourth day of treatment and continuing until the EOS: AM one 25 mg tablet orally; PM two 25 mg tablets orally.
- Dosing will be adjusted based on reported side effects.

5.4 Dose Adjustment Procedures

Dose adjustments for hydroxyzine will be performed by licensed medical providers based on adverse effects reported by participants (e.g. daytime sedation...stop the AM dose of hydroxyzine, difficulty waking in the am...decrease nighttime dose of hydroxyzine). Participants will be contacted with a follow-up call by Research Medical Staff within 72 hours of any dose adjustment.

5.5 ACCOUNTABILITY AND COMPLIANCE

5.5.1 Dispensing Product

The hydroxyzine will be dispensed by the Investigator or designated study staff utilizing blister-pack technology to enhance compliance and accountability. Each dispense and collection of the product will be recorded during each laboratory visit (Visit 2 through Visit 6). All study-related drugs will be expected to be returned by the participant at the End-Of-Study (Visit 7 or early termination).

Prior to dispensing, the site will ensure that the product packaging is labelled with the protocol number and unique participant identifiers, date it was dispensed, and the statements "For investigational use only" and "Keep out of reach of children".

5.5.2 Storage and Accountability

Hydroxyzine will be stored in a climate-controlled secured-storage site (15 degrees C to 30 degrees C) with access limited to authorized personnel only. Full accountability of the distributed products will be ensured by designated staff.

5.5.3 Compliance

Compliance will be ensured by strict distribution of the product, daily SMS messages, and collection of unused products at each study session. This information will be documented in appropriate logs.

6 VARENICLINE

6.1 Description of Varenicline

Varenicline is one of two FDA-approved non-nicotine medications prescribed as a smoking cessation aid. It is a partial agonist of the $\alpha4\beta2$ nACHR. Due to its relatively long half-life, compared to nicotine, varenicline also acts as an antagonist, blocking occupied receptors from additional stimulation from nicotine. Recognized as one of the most effective monotherapy treatments for tobacco dependence, the medication increases the odds of quitting smoking by nearly fourfold compared with placebo. Hays et al. found varenicline to be generally safe and well tolerated as a smoking cessation aid. Common adverse events associated with varenicline (occurring 10% or more) include nausea, insomnia, abnormal dreams, headaches, and nasopharyngitis. ¹⁹ Nausea, the most common side effect of varenicline, has been reported as high as 30%. Abnormal dreams and insomnia have been reported by over 10% of users. $^{27-29}$

6.2 Dosage

- 0.5 mg tablet orally once a day for 3 days.
- Starting on the fourth day, 0.5 mg tablet twice a day, orally.

• After one week, 1.0 mg tablet twice a day, orally.

6.3 Dose Adjustment Procedures

Dose adjustments for varenicline will be performed by licensed medical providers based on adverse effects reported by participants (e.g. insomnia, abnormal dreams, mood disturbances, anxiety...decrease dose to 0.5 mg twice a day for moderate to severe side effects). Participants will be contacted with a follow-up call by Research Medical Staff within 72 hours of any dose adjustment.

6.4 ACCOUNTABILITY AND COMPLIANCE

6.4.1 Dispensing Product

The varenicline will be dispensed by the Investigator or designated study staff utilizing blister-pack technology to enhance compliance and accountability. Each dispense and collection of the product will be recorded during each laboratory visit (Visit 2 through Visit 6). All study-related drug will be collected at the End-Of-Study (Visit 7 or early termination).

Prior to dispensing, the site will ensure that the product packaging is labelled with the protocol number and unique participant identifiers, date it was dispensed, and the statements "For investigational use only" and "Keep out of reach of children".

6.4.2 Storage and Accountability

Varenicline will be stored in a climate-controlled secured-storage site with access limited to the authorized personnel only. Full accountability of the distributed products will be ensured by designated staff.

6.4.3 Compliance

Compliance will be ensured by strict distribution of the product, daily SMS messages, and collection of unused products at each study session. This information will be documented in appropriate logs.

7 STUDY PROCEDURES AND ACTIVITIES

Personnel performing study assessments must have appropriate and documented training. An overview of all study assessments is shown in the schedule of events (Section 8.5). Study personnel will adhere to standard operating procedures (SOPs) for all activities. Appropriate medical advice will be provided to the participant in case of any medical findings requiring health care.

7.1 Informed Consent and Guidance

Prior to any study assessments being performed, the participant will be asked to provide their written consent to participate in the study on an informed consent form (ICF). All assessments must start after the time of ICF signature by the participant.

Designated staff will obtain written consent from each participant under the supervision of the Principal Investigator. The person obtaining consent provides the participants with a written document explaining the procedures and risks and will answer any questions. A signed copy of the informed consent form will be given to

each participant. Participants are informed that they may withdraw from participation in the study at any time without penalty.

Because of the nature of this study and the number of questionnaires that participants are expected to complete, we do not recruit potential participants who do not read, are blind or who do not read/understand English. We are not equipped to validate alternate versions of our questionnaires. Questionnaires cannot be administered orally by a translator or by technicians to illiterate or blind participants because the data obtained would not be comparable to self-administered questionnaires.

7.2 SAFETY LABORATORY AND OTHER ASSESSMENTS

An overview of all assessments is provided in the schedule of events (Section 8.5).

Non-fasting blood samples and urine samples will be collected by qualified and trained site personnel. Participants will be in a seated or in a supine position during blood collection.

The maximal total volume of blood drawn for each participant will be 12.5 ml for clinical chemistry, hematology, and serum pregnancy (for females only).

Samples for clinical chemistry, hematology, urinalysis, and serum pregnancy test will be sent to a central laboratory for analysis. Urine pregnancy and urine drug testing will be performed on-site.

The results of the clinical chemistry, hematology and urinalysis safety panel will not routinely be given to participants. However, if the participant's laboratory results are clinically relevant (including positive pregnancy tests), the medical staff will send the participant a copy of the laboratory results. Participants who are accepted into the study but need medical follow up due to minor abnormalities in laboratory results will also receive a copy of the laboratory results.

